8.6.9. Study Patient Exit

Study patients exit the study when no additional follow-up visits, procedures, or data collection are required. A Study Exit Form must be completed and full source documentation present for the reason(s). A subject may be exited from the study in the following instances:

- Patient signs a consent, surgery is scheduled, but the device is not implanted
- Patient withdraws from the study
- Patient is lost-to-follow-up
- Patient death
- Patient completes all study follow-up

8.7. ADVERSE EVENT REPORTING

Throughout the course of the study, all adverse events will be recorded on the applicable Adverse Event CRF and in the patient's medical records. The seriousness, date of onset, date of resolution, severity, action taken, relationship to the device, and relationship to the procedure will be identified by the Investigator.

8.7.1. General Definitions

An adverse event (AE) is any undesirable clinical occurrence in a patient administered a product and that does not necessarily have a causal relationship with the treatment. An AE can therefore be any unintended sign, symptom or disease temporally associated with the use of an investigational product, whether or not related to the use of the product.

A serious adverse event (SAE) is an AE that results in death, is life threatening, requires in-patient hospitalization or that prolongs hospitalization, results in persistent or significant disability/incapacity, or that is a congenital anomaly or birth defect.

An unanticipated adverse event (UAE) is any serious adverse effect on health or safety or any life threatening problem or death caused by or associated with a device, if that effect, problem, or death was not previously identified in nature, severity, degree of incidence. Additionally, an unanticipated adverse event includes any other unanticipated serious problem associated with a device that relates to the rights, safety, or welfare of subjects.

Severity of an AE is a clinical determination of the event intensity. The severity assessment for a clinical AE should be completed using the following definitions as guidelines:

Mild (+1): Awareness of sign or symptom, but easily tolerated.

Moderate (+2): Discomfort enough to cause interference with usual activity.

Severe (+3): Incapacitating with inability to work or do usual activity.

NOTE: An event that is fatal should be recorded as death on the **ADVERSE EVENT** CRF. The cause of death will be detailed on the **Serious Adverse Events** section of the form.

Relationship to device or procedure of an AE is a judgment determination made by the Investigator that there is a logical connection between device use (e.g., delivery system manipulation) and the occurrence of the AE.

8.7.2. Reporting of Device or Procedure Related Events

For all patients, Investigators shall submit to Endologix and to the reviewing Ethics Committee or IRB a report of any adverse device-related or procedure-related event, including, but not limited to, hospitalization or death within 10 working days after the Investigator first learns of the event. Each of these events will be investigated by Endologix. If it is determined that a UAE has occurred and presents an unreasonable risk to subjects, all investigations or parts of investigations presenting that risk will be terminated. Termination of

the investigation will occur within five (5) working days after notice of the effect is received at Endologix. The terminated investigation will not be resumed without the approval of the ethics committee/IRB.

8.7.3. Reporting of SAEs

Any SAE occurring during the study period must be recorded on the appropriate **ADVERSE EVENT** CRF and **Serious Adverse Events** section of the CRF.

For any SAE, fax the ADVERSE EVENT coversheet and supporting information within 24 hours of awareness to Paragon BioMedical and Endologix. All patients with an SAE must be followed and outcomes reported. The Investigator should supply to Endologix and the responsible ethics committee/IRB with a complete, written case history (AE forms) and any additional requested information (e.g., other diagnostic testing, discharge reports, autopsy reports, etc.).

Deaths

For any patient death, regardless of cause or timing, an autopsy should be requested. If the family has agreed to the conduct of an autopsy, a copy of the autopsy report is required.

A device explant kit will be provided to the hospital for processing and shipment to an independent pathologist per established methods. To request a kit, contact Endologix (see Section 2.1 for contact information).

Every attempt should be made to obtain as much detailed information on the events or conditions leading up to the death as possible. If the patient was hospitalized, a copy of the discharge summary source document is required.

Secondary Interventions

For patients that experience any non-diagnostic invasive secondary treatment of the groin access areas or of the abdominal aortoiliac vessels (e.g., hematoma drainage, vascular exploration for bleeding, iliac stenting, thrombectomy, additional device placement for endoleak, embolization for Type II endoleak, etc.), it is important to identify the area, region or vessel segment that is involved and the specific procedure performed on the relevant **ADVERSE EVENT** CRF. A copy of the discharge summary source document is required.

8.7.4. Anticipated Adverse Events

Adverse events that could potentially occur during this investigation are called anticipated adverse events and are listed in alphabetical order:

- Access site complications and sequelae (e.g., dehiscence, infection, pain, hematoma, pseudoaneurysm)
- Allergic reaction to contrast agent (e.g., pruritus, urticaria, bronchospasm, angioedema, hypotension or anaphylaxis that occurs during or post-procedure)
- Amputation
- Anesthetic complications and sequelae (e.g., aspiration)
- Aneurysm enlargement
- Aneurysm rupture
- Arterial damage or trauma (e.g., bleeding, perforation, dissection, rupture)
- Arterial or venous thrombosis and/or pseudoaneurysm
- Arteriovenous fistula
- Bleeding requiring transfusion and/or surgical intervention
- Bowel complications (e.g., ileus, ischemia, infarction, necrosis)
- Cardiac complications and sequelae (e.g., arrhythmia, myocardial infarction, congestive heart failure, hypotension, hypertension)
- Catheter fragmentation and sequelae (e.g., embolization, vessel trauma)
- Claudication
- Coagulopathy
- Death (due to any cause)
- Edema
- Embolization (micro and macro) with transient or permanent ischemia or infarction
- Endoleak
- Fever and localized inflammation
- Genitourinary complications and sequelae (e.g., ischemia, fistula, incontinence, hematuria, impotence, infection)
- Hepatic failure
- Infection of the aneurysm, device access site, including abscess formation, transient fever and pain.
- Local or systemic neurologic complications and sequelae, transient or permanent (e.g., stroke, transient ischemic attack, paraplegia, paraparesis, paralysis, numbness and/or tingling in legs)
- Lymphatic complications and sequelae (e.g., lymph fistula)
- Thrombosis or occlusion of stent graft or arterial vessel of the lower extremities
- Pulmonary/respiratory complications and sequelae (e.g., pneumonia, respiratory failure, prolonged intubation, pulmonary embolism)
- Renal complications and sequelae (e.g., artery occlusion, infarction, insufficiency, failure)
- Secondary procedure
- Stent graft: improper component placement; incomplete component deployment; component migration; suture break; occlusion/thrombosis; infection; stent fracture; graft material wear; dilatation; erosion; puncture and perigraft flow
- Surgical conversion to open repair

8.7.5. Unanticipated Adverse Events

Investigators shall submit to Endologix and to the reviewing ethics committee/IRB a report of any unanticipated adverse device effect occurring during an investigation as soon as possible, but in no event later than 10 working days after the investigator first learns of the effect. Investigators must submit to Endologix documentation of the report made to the ethics committee.

8.7.6. Protocol Deviations

A protocol deviation is defined as an event where the Investigator or study personnel did not conduct the study according to the clinical protocol or the Clinical Study Agreement. Deviations shall be reported to the Study Sponsor regardless of whether medically justifiable or taken to protect the subject in an emergency. Reports of any deviation from the protocol conducted in an emergency situation, to protect the life or physical well-being of a patient, will be reported to Endologix and to the ethics committee as soon as possible, but no later than 24 hours from the time of the event.

Patient specific deviations and non-subject specific deviations, (e.g. unauthorized use of a study device outside the study, unauthorized use of a study device by a physician who is not listed in the Clinical Study Agreement, etc.) will be reported in writing. Investigators will also adhere to procedures for reporting study deviations to their IRB in accordance with their specific IRB's reporting policies and procedures.

For reporting purposes, deviations may be classified as major (e.g., failure to obtain written informed consent; unauthorized use of study device by a physician who has not completed the Endologix training or who is not on the Study Signature Log) or minor.(e.g., failure to perform a hematocrit blood test; visit outside of window).

Some information collected in this study is not essential to the study endpoints and will not be considered deviation if absent.

8.7.7. Clinical Events Committee Review

Overview

The clinical events committee (CEC) identified in §2 consists of at least three physicians who will serve as independent experts responsible for evaluation and categorization of adverse events reported by the investigators in the trial. Analyses of events described in this protocol will be based on the CEC-determined categorization.

The primary purpose of these individuals is to ensure a consistent, independent review of events and their clinical significance using standardized criteria and definitions. A curriculum vita for each CEC member is maintained by Endologix, and is available for regulatory review. Due to the need for independence, these individuals may not participate in this trial as investigators, and may not hold significant material, financial or other interests which create a potential conflict with respect to this role, including but not limited to significant equity

interest in Endologix.

Process

Endologix will provide independently to the CEC the complete case report form event text that details all deaths and the events as reported by the clinical site investigators. This information will be provided without identification of the site name, and will identify patients by identification number and initials only. Non-serious events or events that are reported as clearly unrelated events will not be assessed by the CEC. The CEC will review events and any follow-up data requested from Endologix. This may include copies of such documents as progress notes, operative notes, discharge summaries, death summaries, and autopsy reports.

The CEC will document the event categorization for each event individually. Meeting notes and supporting information, requests for documentation, etc. will be maintained.

Event Definitions

The following event definitions will be applied to the Primary Endpoint Analysis during this study. Where possible, events will be categorized as being related to the endovascular procedure/bifurcated device, to the fenestrated device, or to the renal stent graft device.

- *Death*: Any death occurring during the study period, regardless of cause.

Death will be further subcategorized as early (within 30 calendar days from the date of the procedure) or late (>30 days). It will also be subcategorized as aneurysm-related or not aneurysm-related.

Aneurysm-related death is defined as: any death occurring within 30 days from the date of the procedure, regardless of cause, and death due to aneurysm rupture or following any procedure intended to treat the aneurysm.

- *Procedural Technical Failure*: An event occurring procedurally or within 30 days post-procedurally that meets one or more of the following criteria:
 - *Aortic Stent Graft Failure* is defined as a failure of the bifurcated or fenestrated proximal extension stent graft to be delivered and deployed, such that the procedure is not completed, or the device failure results in a serious complication, or a residual Type I or III endoleak that cannot be resolved during the index procedure;
 - *Renal Stent Graft Failure* is defined as a failure of the renal stent graft to be delivered and deployed, such that the procedure is not completed, or the device failure results in a serious complication.
- *Major Adverse Event*: An event occurring during the trial that meets one of the following criteria:
 - *All-Cause Death* (see above).
 - *Bowel Ischemia*: the lack of adequate blood flow to the intestines that requires

intensification of medical therapy or surgical/endovascular intervention.

- *Myocardial Infarction*: the presence of raised levels of one or more cardiac biomarkers in comparison to laboratory reference ranges;
 - *Paraplegia*: Paralysis of the lower extremities inclusive of the lower trunk.
 - *Renal Failure*: the need for temporary or permanent dialysis or >0.5mg/dL increase in pre-operative serum creatinine level at two consecutive intervals;
 - *Respiratory Failure*: pneumonia or respiratory failure requiring ventilator support beyond 24 hours post-procedure;
 - *Stroke*: a sudden development of neurological deficit due to vascular lesions of the brain such as hemorrhage, embolism, or thrombosis that persists for >24 hours.
 - *Blood Loss >1,000cc*: Estimated blood loss during the index procedure $\geq 1,000$ cc.
- *Other Definitions*:
- *Aneurysm Enlargement*: Core Lab reported aneurysm sac diameter increase of >5mm in late follow-up as compared to the initial post-operative measurement.
 - *Aneurysm Rupture*: internal bleeding or leaking of blood from the aneurysm subsequent to the index procedure.
 - *Conversion to Open Repair*: open surgical repair of the abdominal aortic aneurysm due to unsuccessful delivery or deployment of the stent graft, due to complications or other clinical situations that precluded successful endovascular treatment, or at any time following initial successful endovascular treatment for any reason.
 - *Cardiac Morbidity*: acute myocardial infarction (diagnosed based on measured levels of one or more cardiac biomarkers in comparison to laboratory reference ranges); new onset heart failure (an acute episode or exacerbation of existing low cardiac output accompanied by distal and/or pulmonary edema); intractable or malignant arrhythmia requiring cardioversion or pacemaker placement; or coronary intervention (coronary artery bypass grafting [CABG] or percutaneous coronary intervention [PCI]).
 - *Clinically Significant Device Migration*: Core Lab reported aortic stent graft movement >10mm from the original implant location resulting in an intervention or in a serious complication.
 - *Renal Dysfunction*: a reduction in the estimated glomerular filtration rate (eGFR) of >30% from the preoperative value;
 - *Secondary Procedure*: any non-diagnostic intervention after the index procedure intended to correct or repair an endoleak, limb occlusion, migration, aneurysm sac expansion and/or a device defect;
 - *Stent Graft Occlusion*: Intervention for aortic or renal stent graft occlusion or as reported by the Core Laboratory.

- *Transient Ischemic Attack*: a sudden development of neurological deficit due to vascular lesions of *the* brain such as hemorrhage, embolism, or thrombosis that persists for <24 hours.
- *Type I/III/IV Endoleak*: Core Lab reported endoleak: between the endograft and the vessel either at the proximal attachment point (Type IA) or at the distal attachment point (Type IB); between endograft components (Type III); or transgraft (Type IV)
- *Type II Endoleak*: Core Lab reported endoleak emanating from a patent collateral vessel (e.g., inferior mesenteric artery; lumbar artery; etc.).

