6. RESPONSE MEASURES

6.1. SAFETY

The safety endpoint is defined as the incidence of Major Adverse Events (MAE), defined as the composite of the following as determined by the independent Clinical Events Committee (CEC). Event definitions are provided in §8.7.7.

- *All-Cause Mortality;*
- *Bowel Ischemia;*
- *Myocardial Infarction;*
- *Paraplegia;*
- *Renal Failure;*
- *Respiratory Failure;*
- *Stroke;*
- *Blood Loss >1,000cc*

Refer to §10.6 for primary safety endpoint analysis details.

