If the variable is categorical, the correlation of the cases with other covariates will be evaluated to determine if there is a relationship between the value of the variable with missing data and a function of other covariates used in the analysis that results in ordinal integer values (perhaps the sum of a subset of several covariates that are present could be used). If there is a significant correlation between the variable with missing values and the function, a cross tabulation of the subjects with scores for the variable with missing data and the function values will be formed. The value of the missing observation will be assigned by generating a uniform random number and comparing that random number to the relative marginal frequency of the distribution of observed values for the given score of the function. If no function can be found to be correlated with the data, the values will be assigned by simple random selection with replacement from subjects with values within treatment groups.

The model will be obtained by including all covariates in the model. The final propensity model will contain all covariates for the first evaluation of balance. The propensity score analysis will be done without knowledge of MAE results for the test group. This is made possible by the fact that test group MAEs are determined by an independent Clinical Events Committee; their adjudicated results are not part of the clinical database but are separately maintained in a dedicated CEC database.

The data will be divided into quintiles. Within the quintiles, the baseline characteristics are evaluated by comparing each characteristic between the test and control groups and observed to determine if a characteristic for which a statistically significant difference was observed

without adjustment is no longer statistically significant. An analysis of balance will be done by the method recommended by Rosenbaum and Rubin.¹⁸ For each continuous or ordinal covariate, an analysis of variance with two treatment groups and five stratum class variables will be done. An examination of the F-tests across and within strata will be examined.

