- d) *Core Lab and Independent Physician Assessor*: The Core Lab is responsible for the processing and assessment of all submitted CT scans preoperatively and imaging postoperatively and for reporting of results. The independent physician assessor is responsible for evaluating the Core Lab processed baseline CT scan to determine patient anatomical suitability for enrollment. In addition, for patients deemed anatomically eligible, the independent physician assessor is responsible for recommending the size of renal stent graft for each artery.
- e) *Data Management Group*: The data management group is responsible for database development, validation, control and management of input from monitored CRFs, maintenance, and reporting for statistical analysis.
- f) *Clinical Events Committee*: The independent clinical events committee will consist of at least three physician members and is responsible for review of events and complications documented on CRFs and in source documents by the study investigators during the trial, and for

- categorization of these events according to the event definitions and primary endpoint criteria in this protocol. Reviews will occur on an ongoing basis throughout the trial as events are reported. The adjudicated events will be reviewed by the Data Safety Monitoring Board.
- g) *Data Safety Monitoring Board (DSMB)*: Consistent with the U.S. FDA guidance document *Establishment and Operation of Clinical Trial Data Monitoring Committees*, Endologix has established a DSMB having pertinent expertise to review on a regular basis adjudicated safety data accumulated and trial progress (i.e., enrollment among groups; completeness and timeliness of data; protocol deviations; etc.) from its ongoing clinical investigations. The DSMB consists of five members, two of which must be physicians with specialty training in endovascular repair. One member of the DSMB is a statistician. The DSMB will be convened to review interim data accumulated during the trial and to render a recommendation for enrollment in the trial: continue; amend; suspend; or, terminate. All action items discussed during the meeting will be documented in the minutes, with agreed upon target completion dates for resolution. The final meeting minutes will be distributed to all DSMB members. Endologix will disclose the recommendations of the DSMB to the US FDA in its annual progress reports to the IDE.

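### Section 8.7.7 keeps non-serious and reported-unrelated events from the CEC, although the CEC determines the primary 30-day MAE endpoint and the MAE definitions carry no such limit

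*Combined protocol and SAP*

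**What the plan says.** Section 6.1 describes the safety endpoint as the MAE rate, "defined as the composite of the following as determined by the independent Clinical Events Committee (CEC"). The 30-day time point comes from the synopsis and section 10.6.1. The overview in section 8.7.7 adds: "Analyses of events described in this protocol will be based on the CEC-determined categorization". Section 10.6.3 repeats that "test group MAEs are determined by an independent Clinical Events Committee", and says the adjudicated results are kept in a separate CEC database and not in the clinical database.

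Section 11.1(f) gives the CEC a broad remit. It "is responsible for review of events and complications documented on CRFs and in source documents by the study investigators during the trial". The same item also has the committee sort what it reviews by the protocol's definitions and endpoint criteria, and it names no limit by seriousness or relatedness.

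The Process paragraph of section 8.7.7 narrows this: "Non-serious events or events that are reported as clearly unrelated events will not be assessed by the CEC".

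The grading that drives the exclusion is made at the site. Under section 8.7, seriousness, severity, "relationship to the device, and relationship to the procedure will be identified by the Investigator". Under section 8.7.1 a serious adverse event "is an AE that results in death, is life threatening, requires in-patient hospitalization or that prolongs hospitalization", or causes lasting disability or a congenital anomaly. No blood-loss volume appears there. The MAE definitions in section 8.7.7 set blood loss by volume during the index procedure alone, and attach no seriousness or relatedness condition to any component.

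**The concern.** The rule that decides what the CEC may assess is not the rule that defines the endpoint. Since analyses rest on the CEC's categorization and the adjudicated MAEs sit only in the CEC database, the plan describes no other way for an excluded event to be counted. In an open, single-arm trial, an unblinded site judgement would then decide which events reach the independent committee.

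Blood loss is the main exposure. It was the largest MAE component in the earlier trial, it is defined by a measured volume, and nothing in the definition of a serious event captures that volume. Three other routes exist:

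- Renal failure by creatinine rise is a lesser one. It needs two consecutive raised values, early events close at day 30, and the one-month visit may fall as late as day 44, so the second value can lie outside the endpoint in any case.
- Myocardial infarction is defined by raised biomarkers alone and could also be graded non-serious.
- Read literally, the sentence even bars assessment of a death reported as clearly unrelated, although death counts regardless of cause.

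At stake are the reported MAE rate, its component rates with exact confidence intervals (section 10.6.4), and a like-for-like comparison with the historical surgical controls.

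**Working it through.** **Inputs.** From section 10.6.2 (earlier trial, 30 days): endovascular 16/192 with any MAE, 11 with blood loss; surgical control 44/66 with any MAE, 38 with blood loss. Planning values: test rate 16.6%, control rate 67%, one-sided alpha 0.025, 97 test patients. Fallback performance goal: 56% (section 10.6.4).

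**The plan's own figure.** Section 10.6.2 states 81% power for 97 versus 66 patients with a test rate of 0.434 and a control rate of 0.670. Exact enumeration with a one-sided Fisher test gives 81.0%, so it reproduces.

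**Patients whose only MAE was blood loss.** The table gives component counts, so only bounds are available.

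- Endovascular: the other components total 2 + 3 + 2 + 2 = 9. MAE patients without blood loss number 16 − 11 = 5 and use at least 5 of those 9, so at most 4 fall in blood-loss patients. Blood loss only: 11 − 4 = 7 up to 11 of 16.
- Control: the other components total 4 + 6 + 5 + 0 + 6 + 5 + 1 = 27. MAE patients without blood loss number 44 − 38 = 6, so at most 21 fall in blood-loss patients. Blood loss only: 38 − 21 = 17 up to 38 of 44.

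**Effect on the reported test rate (illustration).** Let f be the assumed share of blood-loss-only MAEs graded non-serious, and b the number of blood-loss-only patients among 16. Reported rate = 16.6% × (1 − f × b/16).

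| f | b = 7 | b = 11 |
|---|---|---|
| 0.25 | 14.8% | 13.7% |
| 0.50 | 13.0% | 10.9% |
| 1.00 | 9.3% | 5.2% |

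This is not an upper bound on the loss. If both renal-failure events were creatinine-only in patients without blood loss, the table allows 11 + 2 = 13 of 16 to be lost: 16.6% × 3/16 = 3.1%.

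**Pass limits with 97 patients.**

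- Against the 56% goal (exact binomial): P(X ≤ 44) = 0.0227 and P(X ≤ 45) = 0.0361, so the limit is 44 (45%).
- Against 44/66 (one-sided Fisher, unadjusted, not the planned propensity-stratified test): p = 0.0218 at 48 and 0.0293 at 49, so the limit is 48 (49%).
- At the planned rate, 0.166 × 97 is about 16 events. Fisher p = 6.6 × 10⁻¹¹ at 16, and 16 lies far below 44, so both pass with or without lost events.

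**If the device were no better than the comparator.** With an assumed share L of test-group MAE patients never adjudicated, the chance of passing is:

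| L | True rate 0.67, versus 66 controls (unstratified pooled z) | True rate 0.56, versus 56% goal |
|---|---|---|
| 0 | 2.4% | 2.3% |
| 10% | 13.5% | 18.6% |
| 20% | 40% | 59% |
| 30% | 73% | 91% |

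**Control side.** If every blood-loss-only control patient were removed, 44/66 (67%) would become 44 − 38 = 6 to 44 − 17 = 27 of 66 (9% to 41%). This shows how sensitive the comparator is to the counting rule; it is not a forecast.

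**The case against.** The exclusion can be read as a specific triage rule under the general statements in sections 6.1 and 11.1(f), neither of which says that every event must be referred. The same paragraph gives the CEC the full case report form text on deaths and reported events, and the CEC may ask for operative notes. But receiving text is not assessing it, and the sentence says these events will not be assessed. The conflict is softened, not removed.

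Other checks exist: sponsor investigation of device- or procedure-related events (8.7.2), Medical Monitor review of serious events and monitoring against hospital records (11.1), and medical advisory board review of device-related events (11.1(h)). Estimated blood loss is also summarized with its maximum (10.8.2), so a discrepancy could be noticed. None of these determines an MAE or amends the exclusion, and the Medical Monitor's review is itself limited to serious events.

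Several points stand. Index-procedure blood loss could hardly be reported as clearly unrelated to the procedure, so the non-serious limb carries most of the weight. The share graded non-serious is unknown, and the event mix is borrowed from a population that the plan itself describes as less complex. At a true 16.6%, the chance of 45 or more MAEs in 97 is about 8 × 10⁻¹², so the verdict is not at risk at the planned rate. The case report forms are not shown, and a referral flag there cannot be ruled out, although it would still contradict 8.7.7. Finally, patient-level control data are said to be available, but the plan does not say that they include seriousness or relatedness grades.

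**Conclusion.** The concern holds: the exclusion in section 8.7.7 is wrong as written, because it can remove from assessment events that meet the MAE definition. It should be fixed. The contradiction rests on the text alone; the size rests on assumptions.

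The likely harm is an understated MAE rate and blood-loss component. The tabulated reductions depend on the assumed share graded non-serious and on the earlier trial's mix carrying over. Pass or fail would be affected only if the device performed far worse than planned, with a true count above about 44 or 48 of 97; there, an assumed loss of 10% to 30% would raise the false-pass rate sharply.

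The plan does not say how the 44/66 control MAEs were ascertained. If they were unfiltered, applying 8.7.7 as written to the test group can only favour the device. If they were filtered, counting all test-group events would bias against it. Propensity scores balance baseline covariates and cannot repair a difference in ascertainment.

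**What to change.** 1. Before or together with the text change, establish how the 44/66 control MAEs were identified (by seriousness, by relatedness, or from recorded values), so that both groups are counted by one rule.
2. In section 8.7.7 replace the exclusion with: *The CEC will assess every event that may meet an MAE component, regardless of seriousness or reported relatedness.* This also covers biomarker-only myocardial infarction and deaths reported as unrelated.
3. Add a referral rule based on data already collected: recorded blood loss of 1,000 cc or more, a creatinine rise above 0.5 mg/dL, and any reported event matching another component.
4. Reconcile section 8.7.7 with 11.1(f).

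The cost is one sentence, a data-driven referral listing, a modest number of extra cases for the existing committee, and a check of the control records, which may prove incomplete on grading. The reported MAE rate may be less favourable. The sample size of 97, the 81% power at a test rate of 0.434 and the one-sided alpha of 0.025 are unchanged.
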